5 PRIMARY, SECONDARY AND EXPLORATORY ENDPOINTS

5.1 Primary Endpoint

The Primary evaluation parameter is:

- Change from baseline in the peak esophageal intraepithelial eosinophil count at Week 4.

5.2 Secondary Endpoints

- Absolute change in DSQ score from baseline (see DSQ score definition in Section 7.7.2)
- Proportion of participants achieving peak esophageal intraepithelial eosinophil count of < 15 eos/hpf (Week 4)
- Percent reduction in peak esophageal intraepithelial eosinophil count (eos/hpf) (Week 4)
- The safety endpoints are Monitoring of AEs, physical examinations, vital signs, electrocardiograms (ECGs), clinical laboratory tests, and clinical evaluations. Participants will be asked to monitor all AEs experienced from the time of informed consent until their last study visit.

5.3 Exploratory Endpoints

- Proportion of participants achieving peak esophageal intraepithelial eosinophil count of \leq 6 eos/hpf (400 \times) at Week 4
- Proportion of participants achieving peak esophageal intraepithelial eosinophil count of \leq 1 eos/hpf (400 \times) at Week 4
- Relative change in the EDP transcriptome signature (Week 4)
- Relative change in immune cells and markers of inflammation pre- and postdose administration at screening, baseline, and Weeks 1, 2, 4, 6, and 8. Immune cells and markers of inflammation include: immune cell phenotyping (T-subsets, B-subsets, and macrophage subsets); A20; serum cytokines; serum IgE/IgG4; and serum eosinophil derived neurotoxin (EDN) for eosinophil activation.
- Absolute change in EoE-EREFs (Week 4)

- Absolute change in EoE grade score from the EoE Histology Scoring System (EoEHSS) (Week 4)
- Absolute change in EoE stage score from the EoEHSS (Week 4)
- Proportion of participants with use of rescue medications or procedures (up to Week 8)
- Concentration of functional IRL201104 (up to Week 8)
- Incidence of treatment-emergent antidrug antibody (ADA) responses (Week 8)
- Absolute days without dysphagia.
- Change in PGI-S and PGI-C.

Note that an additional exploratory endpoint: absolute change in severity and/or frequency of EoE symptoms other than dysphagia (up to Week 8) was included in the protocol but will not be evaluated because the relevant information is being captured only as part of the screening visit evaluation. It was inadvertently left in the most current version of the protocol.

6 ANALYSIS POPULATION AND TREATMENT GROUPS

6.1 Analysis Population

Full Analysis Set: The full analysis set (FAS) will consist of all participants randomized at baseline who receive at least one dose of treatment and who had a baseline and at least one post-baseline measure of the primary or any one of the secondary endpoints. Efficacy evaluations will consider participants according to the treatment group to which they were assigned.

Safety Analysis Set: The safety analysis set will include all participants who were documented to have taken at least 1 dose of study treatment. Safety evaluations will consider participants according to the actual treatment they received.

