15.2. Analysis Populations

15.2.1. Full Analysis Set

The full analysis set (FAS) will consist of all participants randomized at baseline who receive at least one dose of treatment.

This is the principal data set for the formal evaluation of the primary and secondary efficacy endpoints at Week 4. Participants will be evaluated based on the treatment group to which they were randomized.

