15.3. Planned Analysis

15.3.1. Study Population Analysis

Demographics and baseline disease characteristics and medical history will be summarized descriptively by treatment group. Participant disposition will be summarized, including the reasons for discontinuation. The number of participants in each analysis population will be displayed and an accounting of exclusions from each study population will be provided.

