3 DATA ANALYSIS CONSIDERATION

Output processing will be undertaken by [REDACTED], using SAS Version 9.3 (or higher). All Tables, Listings and Figures (TLFs) will be produced in landscape format. In general, all data will be listed by the participant and visit. The number of variables presented in each listing can vary. Please refer to mock tables, listings and figures.

No formal statistical analysis will be conducted for this study. Summary statistics appropriate for categorical and continuous variables will be presented by treatment group and all inferences will be based on clinical evaluation of those results.

Data will be summarized by treatment group where appropriate. The total number of participants (N) in each treatment group under the stated population will be displayed in the header of summary tables.

Continuous data will be summarized using descriptive statistics for continuous variables. Unless otherwise stated, descriptive statistics will include the number of participants (n), mean, standard deviation (SD), minimum, median and maximum. When n=0, summary statistics (other than n) will be displayed as blank fields. When n=1, only the minimum and maximum will be reported; all other summary statistics will be displayed as blank entries. The number of missing values associated with an n that is less than the expected n for the visit or time point of interest will also be presented.

For summary tables of categorical variables, counts and percentages will be presented. The count [n] indicates the actual number of participants with a particular value of a variable or event, which should always be less than or equal to the total number of participants in the respective treatment group [N]. The number and percentage of participants with missing values for a variable/category/event will also be presented for the resulting visits/time points under the “Missing” category.

Percentage will be obtained by: $\% = (n/N) * 100$.

All dates will be displayed in DDMMYY format.

Decimal Precision Convention:

The minimum and maximum statistics will be presented to the same number of decimal places as the original data. The mean and median will be presented to one more decimal place than the original data, whereas the standard deviation will be presented to two more decimal places than the original data. Unless otherwise stated, all percentages will be expressed to one decimal place.

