7 ANALYSIS METHODS AND REPORTING DESCRIPTIONS

7.1 Disposition

Participant disposition will summarize the number and percentage of participants included in the FAS and Safety Analysis Sets, along with a summary of those who completed the study and those who discontinued from the study along with the reasons for discontinuation from study by treatment group using FAS. Study discontinuation will also be summarized by study week interval (through Week 1, >Week 1 through Week 2, >Week 2 through Week 4, and >Week 4 through Week 8).

A listing of participant disposition will be also presented describing all details of the reason for discontinuation, investigator comments, date and study day from randomization of the discontinuation, and any other relevant information, e.g., adverse events or other information that determined the grounds for discontinuation.

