7.2 Demographic and Baseline Characteristics

Demographic and baseline characteristics will include age (years), sex, ethnicity, race, data for childbearing potential, height (cm), weight (kg) and BMI (kg/m²) of the participants and will be summarized by treatment group for the FAS and repeated for the Safety Analysis Set if the two sets are different.

Descriptive statistics (n, mean, SD, minimum, median, and maximum) will be generated for continuous variables and the number and percentage of participants in each class of the categorical variables will be tabulated.

All individual participant demographic and baseline characteristics data will be listed by treatment group.

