For each DSQ calculation, the sum of the specified question(s) from each reported daily diary with non-missing data over the interval being reported will be obtained, dividing this by the number of reported daily diaries with non-missing data in that same interval. This result will then be multiplied by the interval. This normalizes each DSQ sum over the interval. For the DSQ score, if a response of “No” is recorded for Question 2, the DSQ score will be set to zero for that day. The DSQ calculations during the interval being reported prior to the baseline visit will be defined as the baseline DSQ evaluation. For each 14-day period, at least 8 reported diaries are needed to effectuate a DSQ calculation for that period. If at least 8 diaries are not available, the DSQ result for that 14-day period will be set to missing.

The absolute change in DSQ score from baseline will be summarized as the n, mean, standard deviation, median, minimum, and maximum by treatment group.

Additionally, exploratory endpoint analysis of absolute days without dysphagia will be summarized as the n, mean, standard deviation, median, minimum, and maximum by treatment group. Absolute days without dysphagia will be obtained through a counting process of the number of DSQ records between baseline and Week 8 that the participant reports DSQ question #2 as “No.”

Esophageal intraepithelial Eosinophil

The proportion of participants achieving peak esophageal intraepithelial eosinophil count of < 15 eos/hpf (Week 4) will be summarized using frequency and percentage.

Also, percent reduction in peak esophageal intraepithelial eosinophil count (eos/hpf) (Week 4) will be summarized as the n, mean, standard deviation, median, minimum, and maximum by treatment group.

Also, exploratory endpoint analysis will be performed for esophageal intraepithelial eosinophil. The proportion of participants achieving peak esophageal intraepithelial eosinophil count of ≤ 1 and ≤ 6 eos/hpf (400 \times) at Week 4 will be summarized separately using frequency and percentage.

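### SAP 6.1 narrows the protocol's full analysis set without declaring it, and SAP 7.1 then reports who left the study on that narrower set

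*SAP*

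**What the plan says.** Protocol 15.2.1 defines the FAS as "all participants randomized at baseline who receive at least one dose of treatment", analysed as randomised. SAP 6.1 starts from the same group but adds a condition: only participants "who had a baseline and at least one post-baseline measure of the primary or any one of the secondary endpoints". The SAP does not define a measure. SAP 5.2 lists safety monitoring among the secondary endpoints ("The safety endpoints are Monitoring of AEs, physical examinations, vital signs" and so on), so the condition can be read broadly or narrowly.

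SAP Section 11, which lists changes to the protocol's analyses, covers only the EDP transcriptome and the immune markers. The note in SAP 5.3 declares one further change, to an exploratory symptom endpoint. Neither mentions the FAS. SAP Section 1 gives the SAP precedence where the two documents disagree on statistical analysis.

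SAP 7.1 tabulates completion, discontinuation and "reasons for discontinuation from study by treatment group using FAS". A separate sentence breaks discontinuation down by study week and names no set. SAP 7.2 foresees that the FAS and the Safety Analysis Set may differ and has demographics "repeated for the Safety Analysis Set if the two sets are different"; SAP 7.1 has no matching repeat for disposition. Protocol 15.3.1 says that "an accounting of exclusions from each study population will be provided". SAP 7.1 keeps the number in each set, but no SAP section provides for the reasons for exclusion.

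**The concern.** A table of who left, when and why should not rest on a set whose membership can depend on staying long enough to produce data. Early exit may be related to treatment: Protocol 8.3.1 names intolerance as a ground for withdrawal by the investigator. SAP 2.4 also replaces participants who leave without all three doses and the final endoscopy, so an arm can refill to its planned size while the person replaced is absent from the by-arm table.

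The study has no formal inference. SAP Section 3 rests every conclusion on clinical reading of the summary tables, and with about 12 participants per arm one or two people visibly change a percentage. What is at stake is a complete by-arm count of discontinuations with reasons, and the denominators of FAS proportions, chiefly the responder proportion.

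**Working it through.** **1. The plan's own figure.** SAP 2.3 and 2.4 give 36 completers at 1:1:1, so 36/3 = 12 per arm. There is no power calculation to reproduce. Up to 50 may be enrolled, but the documents do not separate screening losses from dropout, so 50 − 36 = 14 is not a dropout rate. All counts of leavers and responders below are assumptions.

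**2. Who is in which set.**

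| Participant | Protocol FAS | SAP FAS, broad reading (safety assessment or a single diary counts) | SAP FAS, narrow reading (computed DSQ score or Week 4 biopsy) |
|---|---|---|---|
| Randomised, never dosed | out | out | out |
| Dosed, leaves the study before Visit 2 | in | in, almost always | generally out |
| Dosed, leaves at Visit 2 | in | in | depends on the visit day and the DSQ interval |
| Stops treatment, stays to Week 4 assessments | in | in | in |

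On the broad reading the clause excludes almost nobody, because vital signs are due about 15 minutes after the Day 0 dose. The first row does not come from the added clause. It arises because SAP 7.1 uses the FAS at all. Randomisation and first dose are both at Visit 1, so that group should be small.

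**3. When a DSQ score can first exist.** SAP 7.7.2 states that "at least 8 reported diaries are needed to effectuate a DSQ calculation for that period", for 14-day periods. Diaries are completed in the evening, so a Visit 2 on Day *v* is preceded by *v* post-dose diaries (evenings of Day 0 to Day *v* − 1). The ±3-day window puts Visit 2 between Day 4 and Day 10:

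- Visit on Day 4: 4 post-dose diaries; on Day 7: 7. Both are below 8.
- Visit on Day 8: 8 post-dose diaries; on Day 10: 10. Both meet the minimum.
- If the interval is the 14 days before the visit, it also takes in 14 − *v* pre-dose days (7 for a Day 7 visit), and a score is possible for any visit day.

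Someone who attends Visit 2 may therefore have a score even on the narrow reading. The people at risk of exclusion are mainly those who leave completely before it.

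**4. Effect on the discontinuation table.** Assume 12 completers in an arm plus *d* dosed early leavers, replaced, on the narrow reading. The protocol FAS gives *d*/(12 + *d*); the SAP FAS gives 0/12.

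- *d* = 1: 1/13 = 7.7% against 0/12 = 0.0%
- *d* = 2: 2/14 = 14.3% against 0/12 = 0.0%

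**5. Effect on the responder proportion (below 15 eos/hpf).** SAP Section 3 divides by N of the stated population. With 6 responders assumed:

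- *d* = 1: 6/13 = 46.2% on the protocol FAS against 6/12 = 50.0% on the SAP FAS, 3.8 points
- *d* = 2: 6/14 = 42.9% against 50.0%, 7.1 points

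**6. Effect on the primary summary.** SAP Section 3 imputes no missing efficacy values, so a participant without a Week 4 biopsy contributes no change score under either definition. The difference in mean change is 0.

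**The case against.** The strongest reply is that the literal text does no harm. SAP 6.1 accepts any one secondary endpoint, SAP 5.2 puts safety monitoring under that heading, and on that reading every dosed participant stays in. Harm needs the narrower reading and early leavers whose number the documents do not give. Participants who stop treatment or are rescued are asked to keep attending (Protocol 8.3.1 and 9.2.3), which leaves few complete early exits. The disposition listing is not restricted to the FAS and gives reasons, dates and study days; the set counts are reported; and the primary and secondary endpoints are repeated on the SAS, apparently the Safety Analysis Set. The SAP is to be read together with the protocol, so its silence does not cancel the accounting of exclusions, and the mock tables it refers to may supply it. The protocol names no set for disposition, so an all-randomised base could be called a preference.

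Most of this stands and limits the size. It does not remove the point. The change of definition is real, undeclared and prevails over the protocol, and two programmers could build different sets from the same words. On either reading, undosed randomised participants are missing from the discontinuation table. A listing lets a reader rebuild the by-arm count but does not replace it.

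Three stronger inferences are tempting and not supported:

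- That the first study-week row would be empty by construction. The study-week sentence names no set, and the broad reading keeps early leavers in.
- That nobody who leaves at Visit 2 can have a DSQ score. The visit window and the possible reach of the interval before Day 0 say otherwise.
- That the set-membership table would show percentages above 100. SAP Section 3 says that n "should always be less than or equal to the total number of participants in the respective treatment group", and SAP 7.1 does not say that the FAS is the base for those percentages.

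**Conclusion.** The point holds in a limited form. SAP 6.1 narrows the protocol FAS without declaring it, and SAP 7.1 places the by-arm account of completion and discontinuation on that set. Randomised but undosed participants are missing on any reading. Dosed participants who leave altogether before a DSQ score or biopsy exists are missing only if measure means one of those; if safety assessments count, the loss among dosed participants is close to zero.

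On the narrow reading, with 12 completers per arm and one or two early leavers assumed, the table shows 0% where 7.7% or 14.3% left. With 6 assumed responders, the FAS responder proportion is 3.8 or 7.1 points higher than on the protocol FAS. A reader might infer that the primary result is biased by the narrower set; it is not, because the mean change is the same under both definitions. The case for acting is that the better rule costs almost nothing and helps on either reading.

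**What to change.** 1. In SAP 7.1, base completion, discontinuation, reasons and the study-week breakdown on all randomised participants, state that number as N for each arm, and identify replaced participants.
2. In SAP 6.1, delete the added baseline and post-baseline clause and restore the protocol FAS: all randomised and dosed, analysed as randomised. If the sponsor prefers to keep the clause, define what counts as a measure and declare the change in Section 11.
3. As housekeeping, add the accounting of exclusions from each set promised in Protocol 15.3.1, by arm and reason, and write out SAS in SAP 7.7.1 and 7.7.2, since Section 3 also uses that name for the software.

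The cost is a few lines of SAP text and one table, with no new data. FAS responder percentages may come out slightly lower.

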6.2 Treatment Groups

Participants will be randomized 1:1:1 to 4 mg or 8 mg IRL201104 or placebo respectively. Participants will receive a dose of IRL201104 4 mg IV with endoscopy, IRL201104 8 mg IV with endoscopy or Placebo IV with endoscopy.

The 3 Arms will be labelled as “**IRL201104 4 mg IV**”, “**IRL201104 8 mg IV**” and “**Placebo**” in respective header of TLFs.

The below table includes the treatment labeling for all Tables, Listings and Figures (wherever as appropriate):

Treatment	Treatment Label for TLF
IRL201104 4 mg IV with endoscopy and esophageal biopsy 2 weeks after last dose (Week 4).	IRL201104 4 mg IV
IRL201104 8 mg IV with endoscopy and esophageal biopsy 2 weeks after last dose (Week 4).	IRL201104 8 mg IV
Placebo IV with endoscopy and esophageal biopsy 2 weeks after last dose (Week 4)	Placebo
All treatments	Overall

7 ANALYSIS METHODS AND REPORTING DESCRIPTIONS

7.1 Disposition

Participant disposition will summarize the number and percentage of participants included in the FAS and Safety Analysis Sets, along with a summary of those who completed the study and those who discontinued from the study along with the reasons for discontinuation from study by treatment group using FAS. Study discontinuation will also be summarized by study week interval (through Week 1, >Week 1 through Week 2, >Week 2 through Week 4, and >Week 4 through Week 8).

A listing of participant disposition will be also presented describing all details of the reason for discontinuation, investigator comments, date and study day from randomization of the discontinuation, and any other relevant information, e.g., adverse events or other information that determined the grounds for discontinuation.

7.2 Demographic and Baseline Characteristics

Demographic and baseline characteristics will include age (years), sex, ethnicity, race, data for childbearing potential, height (cm), weight (kg) and BMI (kg/m²) of the participants and will be summarized by treatment group for the FAS and repeated for the Safety Analysis Set if the two sets are different.

Descriptive statistics (n, mean, SD, minimum, median, and maximum) will be generated for continuous variables and the number and percentage of participants in each class of the categorical variables will be tabulated.

All individual participant demographic and baseline characteristics data will be listed by treatment group.

7.3 Medical History

Medical history will be coded using Medical Dictionary for Regulatory Activities (MedDRA) version 24.0.

Medical/Surgical history will be summarized by treatment group with the number and percentage of participants in each system organ class (SOC), preferred term (PT), and overall, on the Safety Analysis Set. Participants will be counted only once at the PT, only once at the SOC, and only once at participant level for the counting of total number of participants with a medical history term.

Listings of medical history events for participants in the Safety Analysis Set will be provided.

EOE-specific medical history of participants will be listed and summarized separately.

7.4 Prior and Concomitant Medications

Prior Medications

Prior medications are those medications that are taken before the ICF signed. i.e., prior medications have a stop date/time before ICF signed. Medications stopped on the same day as the ICF signed will be considered as prior medication only.

Concomitant Medications

Any treatment (including nutritional supplements) or procedure administered from the time of informed consent to the end of the final study visit is considered concomitant medication/procedures. This includes medications that were started before the study and are ongoing during the study.

Prior and concomitant medication will be categorized by preferred name and ATC level 4 class per World Health Organization Drug Dictionary (WHODRUG; Version 01MARCH GLOBAL 2021), will be summarized overall for the Safety Analysis Set. If ATC level 4 class is missing, we will use highest non missing available ATC level data. The number and percentage of participants using each medication will be displayed together with the number and percentage of participants using at least one medication.

All prior and concomitant medications will be presented in separate listings for the Safety Analysis Set.

7.5 Protocol Deviation

A summary table of protocol deviations will be presented by treatment group using the Safety Analysis Set. A listing of participants with protocol deviations will be presented along with the specific deviation(s) and recorded time/visit of the deviation(s) for each participant.

7.6 Study Drug Exposure

A listing will be provided for study drug administration information, including date and time of IRL201104 4 mg and 8 mg and placebo administration using the Safety Analysis Set. That listing will also contain, if applicable, relevant information recorded by the investigational site that describes or otherwise explains deviations from the protocol not already captured in the protocol deviation listing. Such information may be included as part of a post-hoc appendix to the clinical study report (CSR).

